9.2. Methods and Timing for Assessing, Recording, and Analyzing Safety Parameters

9.2.1. Adverse Events

Adverse Event:

ICH E6 defines an AE as any untoward medical occurrence in a patient or clinical investigation subject administered a pharmaceutical product regardless of its causal relationship to the study treatment. FDA defines an AE as any untoward medical occurrence associated with the use of a drug in humans, whether or not considered drug related.

An AE can therefore be any unfavorable and unintended sign (including an abnormal laboratory finding), symptom, or disease temporally associated with the use of medicinal (investigational) product. The occurrence of an AE may come to the attention of study personnel during study visits and interviews of a study recipient presenting for medical care, or upon review by a study monitor.

AEs, including solicited local (injection site) and systemic (subjective and quantitative) reactions, will be captured on the appropriate data collection form and eCRF. Information to be collected for unsolicited non-serious AEs includes event description, date of onset, assessment of severity, relationship to study product and alternate etiology (assessed only by those with the training and authority to make a diagnosis and listed on the Form FDA 1572 as an investigator), date of resolution, seriousness and outcome. FWs will be trained on the assessment of local and systemic reactogenicity. If the subject reports an AE that is either not included among the solicited AEs or is a grade 3 solicited AE, then the FW will contact a study clinician. The study

clinician will either visit the participant at home or the participant will be referred to the study health center based on the FW's assessment. AEs occurring during the trial collection and reporting period will be documented appropriately regardless of relationship. AEs will be followed through resolution.

Any medical condition that is present at the time that the subject is screened will be considered as baseline and not reported as an AE. However, if the severity of any pre-existing medical condition increases, it should be recorded as an AE.

All AEs must be graded for severity and relationship to study product (see definitions). Adverse events characterized as intermittent require documentation of onset and duration of each episode. The start and stop date of each reported AE will be recorded on the appropriate data collection form and eCRF.

Severity of Event: AEs will be assessed by the investigator using a protocol-defined grading system (toxicity table included as an appendix). For events not included in the protocol-defined grading system, the following guidelines will be used to quantify severity:

- Mild (Grade 1): Events require minimal or no treatment and do not interfere with the subject's daily activities.
- Moderate (Grade 2): Events result in a low level of inconvenience or concern with therapeutic measures. Moderate events may cause some interference with functioning and daily activities.
- Severe (Grade 3): Events interrupt the subject's daily activities and may require systemic drug therapy or other treatment. Severe events are usually incapacitating.

Changes in the severity of an AE should be documented to allow an assessment of the duration of the event at each level of intensity to be performed. Adverse events characterized as intermittent require documentation of onset and duration of each episode.

Relationship to Study Products: The assessment of the relationship of an AE to the administration of study product is made only by those with the training and authority to make a diagnosis and listed on the Form FDA 1572 as an investigator based on all available information at the time of the completion of the eCRF. Whether the AE is related or not, is not a factor in determining what is or is not reported in this trial. If there is any doubt as to whether a clinical observation is an AE, the event should be reported.

In a clinical trial, the study product must always be suspect. To help assess, the following guidelines are used.

- Related – There is a reasonable possibility that the study product caused the adverse event. Reasonable possibility means that there is evidence to suggest a causal relationship between the study product and the adverse event.
- Not Related – There is not a reasonable possibility that the administration of the study product caused the event.

9.2.2. Reactogenicity (for Vaccine Studies and Some Therapeutic Trials)

Reactogenicity events are AEs that are common and known to occur following administration of this type of study vaccine. The following Toxicity Grading Scales will be used to grade solicited local (injection site) and systemic (subjective and quantitative) reactions:

Table 3: Local (Injection Site) Reactogenicity Grading

Local (Injection Site) Reaction	Mild (Grade 1)	Moderate (Grade 2)	Severe (Grade 3)
Pain	Does not interfere with daily activity	Repeated use of non-narcotic pain reliever > 24 hours or interferes with daily activity	Any use of narcotic pain reliever or prevents daily activity
Tenderness	Discomfort only to deep palpation	Discomfort to light palpation or movement	Significant discomfort to any touch or movement
Ecchymosis (Bruising)*	No interference with daily activity	Some interference with daily activity not requiring medical intervention	Prevents daily activity and requires medical intervention
Erythema (Redness)*	Does not interfere with daily activity	Interferes with daily activity	Prevents daily activity
Induration (Hardness)/Edema (Swelling)*	Does not interfere with daily activity	Interferes with daily activity	Prevents daily activity

Ecchymosis (bruising), erythema (redness), and induration (hardness)/edema (swelling) as analyzed by measurement will be graded as follows:

Table 4: Local (Injection Site) Reactogenicity Measurements

Local (Injection Site) Reaction	Small	Medium	Large
Ecchymosis (Bruising)*	1-50 mm	51-100 mm	> 100 mm
Erythema (Redness)*	1-50 mm	51-100 mm	> 100 mm
Induration (Hardness)/Edema (Swelling)*	1-50 mm	51-100 mm	> 100 mm

*Will not be used as halting criteria.

In addition to grading the measured local reactions at the greatest single diameter, the measurements will be recorded as continuous variables.

Table 5: Subjective Systemic Reactogenicity Grading

Systemic (Subjective)	Mild (Grade 1)	Moderate (Grade 2)	Severe (Grade 3)
Feverishness (Chills/Shivering/Sweating)	No interference with daily activity	Some interference with daily activity not requiring medical intervention	Prevents daily activity and requires medical intervention
Fatigue (Tiredness)	No interference with daily activity	Some interference with daily activity	Significant; prevents daily activity
Malaise (General Unwell Feeling)	No interference with daily activity	Some interference with daily activity not requiring medical intervention	Prevents daily activity and requires medical intervention
Myalgia (Body Aches/Muscular Pain)*	No interference with daily activity	Some interference with daily activity	Significant; prevents daily activity
Arthralgia (Joint Pain)*	No interference with daily activity	Some interference with daily activity not requiring medical intervention	Prevents daily activity and requires medical intervention
Headache	No interference with daily activity	Repeated use of non-narcotic pain reliever > 24 hours or some interference with daily activity	Significant; any use of narcotic pain reliever or prevents daily activity
Nausea	No interference with daily activity	Some interference with daily activity	Prevents daily activities
Allergic Reaction	Pruritus without rash	Localized urticaria OR requires oral therapy	Generalized urticaria; angioedema OR anaphylaxis OR requires epinephrine

*Not at injection site.

Oral temperature[#] will be graded as follows:

Table 6: Quantitative Systemic Reactogenicity Grading

Systemic (Quantitative)	Mild (Grade 1)	Moderate (Grade 2)	Severe (Grade 3)
Fever* - oral [†]	38.0 – 38.4°C 100.4 – 101.1°F	38.5 – 38.9°C 101.2 – 102.0°F	> 38.9°C ≥ 102.1°F

[#]Oral temperature assessed on Day 1 prior to study vaccination will be considered as baseline.

*A fever can be considered not related to the study product if an alternative etiology can be documented.

†Subjects must not eat or drink anything hot or cold, or smoke within 10 minutes prior to taking oral temperature.

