7.4.1. Clinic or Home Visits

These visits will occur in person at the clinic or may be conducted by trained field officers at the participants' homes.

7.4.1.1. Post Study Vaccination Follow-up Visit, Day 4 (± 1 d): Home Visit, Pregnant Women (Visit 02 or V02)

- This visit will take place in the clinic or alternatively by trained field workers (FWs).
- Study personnel will obtain interim medical history, including an assessment for new medical conditions by interview of subjects and note any changes since the previous visit.
- Study personnel will review solicited AEs with subjects and assess and record all solicited data, AE/SAEs, unsolicited AEs, and concomitant medications/vaccinations on the appropriate data collection forms. FWs will be trained on the assessment of local and systemic reactogenicity. If the subject reports an AE that is either not included among the solicited AEs or is a grade 3 solicited AE, then the FW will contact a study clinician. The study clinician will either visit the participant at home or the participant will be referred to the study health center based on the FW's assessment.

7.4.1.2. Post Study Vaccination Follow-up Visit, Day 8 ($+3$ d): Home Visit, Pregnant Women (Visit 03 or V03)

- This visit will take place in the clinic or alternatively by trained FWs.
- Study personnel will obtain interim medical history, including an assessment for new medical conditions, by interview of subjects and note any changes since the previous visit.
- Study personnel will review solicited AEs with subjects and assess and record all solicited data, AE/SAEs, unsolicited AEs, and concomitant medications/vaccinations on the appropriate data collection forms. FWs will be trained on the assessment of local and systemic reactogenicity. If the subject reports an AE that is either not included among the solicited AEs or is a grade 3 solicited AE, then the FW will contact a study clinician. The study clinician will either visit the participant at home or the participant will be referred to the study health center based on the FW's assessment.

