9.5. Halting Rules

For pregnant women, further enrollment and study vaccinations will be halted for DSMB review/recommendation if any of the following are reported:

- Any subject experiences ulceration, abscess, or necrosis at the injection site related to study product administration.
- Any subject experiences laryngospasm, bronchospasm, or anaphylaxis within 1 day after administration of study product that is considered related to study product.

- Two or more subjects experience generalized urticaria within 3 days after administration of study product that is considered related to study product.
- Any subject experiences a study vaccine-related SAE from the time of study vaccination through subject's last study visit.
- Any subject experiences acute weakness of limbs and/or cranial nerve innervated muscles (description of potential signal of GBS) after administration of study vaccine.

For pregnant women, this study will also be halted for DSMB review/recommendation if, within 7 days after administration of the study vaccination, any of the following occurs:

- 5% or more of subjects (with a minimum of 5 subjects) who received study vaccine experience the same severe (Grade 3) study vaccine-related injection site reaction.
- 5% or more of subjects (with a minimum of 5 subjects) who received study vaccine experience the same severe (Grade 3) study vaccine-related subjective systemic reaction with the exception of allergic reaction, for which the severity (grade) is corroborated by study personnel.
- 5% or more of subjects (with a minimum of 5 subjects) who received study vaccine experience the same severe (Grade 3) study vaccine-related quantitative systemic reaction.
- 5% or more of subjects (with a minimum of 5 subjects) who received study vaccine experience the same severe (Grade 3) pregnancy-related AEs, as found in [Section 9.2.4](#), that are deemed study-vaccine related.

Grading scales for solicited local (injection site) and systemic (subjective and quantitative) reactions are included in [Section 9.2.2](#). Solicited injection site measurements will not be used to halt the study.

If any of the halting rules are met following any subject receipt of study vaccination, then this study will not continue with the remaining enrollments or study vaccinations without a review by and recommendation from the DSMB to proceed.

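### For feverishness, malaise and arthralgia, an event that stops daily activity but needs no medical intervention meets no severity grade, so it can escape the Grade 3 halting count and clinician call

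*Protocol*

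**What the plan says.** Protocol 9.2.2, Table 5 grades eight subjective systemic reactions. For feverishness, malaise and arthralgia, Grade 1 is no interference with daily activity, Grade 2 is "Some interference with daily activity not requiring medical intervention", and Grade 3 is "Prevents daily activity and requires medical intervention". SAP Table 8 repeats these rows.

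Other rows of Table 5 work differently. Fatigue and myalgia are Grade 3 when "Significant; prevents daily activity" applies. Nausea likewise needs only prevented activity. Headache joins its two Grade 3 conditions with an *or*.

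Protocol 9.2.1 states: "All AEs must be graded for severity and relationship to study product". Its general mild/moderate/severe guideline is limited in scope: "For events not included in the protocol-defined grading system, the following guidelines will be used to quantify severity".

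Three things use the grade:

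- **Halting (Protocol 9.5).** The study halts for DSMB review if, within 7 days of vaccination, 5% or more of vaccinated subjects (at least 5) have one particular kind of "severe (Grade 3) study vaccine-related subjective systemic reaction with the exception of allergic reaction, for which the severity (grade) is corroborated by study personnel". The section refers back to the 9.2.2 scales.
- **Home visits (Protocol 7.4.1, Days 4 and 8).** If the woman reports an event that is not on the solicited list "or is a grade 3 solicited AE, then the FW will contact a study clinician".
- **Reporting.** Frequency and severity of solicited reactions is a primary tolerability outcome (Protocol 3.2.1). SAP 9.3.1 tabulates it by maximum severity (Table 51) and by day (Tables 52 to 54).

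**The concern.** In these three rows the step from Grade 2 to Grade 3 changes two things at once: the degree of interference, and whether intervention is needed. An event that changes only one of them satisfies neither definition. The important case is a woman who is incapacitated but needs no treatment. Her arthralgia has no grade, while equally incapacitating myalgia is Grade 3.

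The general guideline in 9.2.1 does not formally fill the gap, because these reactions are in the grading tables. The documents therefore leave the choice to each assessor, and they do not show which way assessors would go. If the event is placed at Grade 2 it is not counted for halting, does not by itself oblige the field worker to call a clinician, and appears as moderate. If it is left ungraded it may drop out of Table 51, whose percentages use non-missing data as the denominator.

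The clinician call is also partly circular for these rows: the field worker must judge whether medical intervention is required before contacting the person qualified to decide that.

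**Working it through.** **Coverage of the grades.** The plan states no figure to reproduce here. Cross three levels of interference with intervention needed or not, and read each cell against the row wording:

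| Interference | Intervention needed | Feverishness, malaise, arthralgia | Fatigue, myalgia, nausea |
|---|---|---|---|
| None | No | Grade 1 | Grade 1 |
| None | Yes | Grade 1 | Grade 1 |
| Some | No | Grade 2 | Grade 2 |
| Some | Yes | **no grade** | Grade 2 |
| Prevents | No | **no grade** | Grade 3 |
| Prevents | Yes | Grade 3 | Grade 3 |

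Two of six cells are empty in the affected rows and none in the comparison rows. That is 3 of the 8 rows of Table 5. Ecchymosis in Table 3 (1 of 5 local rows) has the same gap, but a footnote excludes it from halting, so only its tabulation and the clinician call are affected.

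**A possible counter-reading.** If *some* interference is taken to include complete prevention, the incapacitating event that needs no treatment becomes Grade 2. It is still outside the halting count and the clinician trigger, and its severity is understated.

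**Effect on the halting rule, as illustration.** Inputs:

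- Threshold from Protocol 9.5: r = max(5, ceil(0.05 n)). This stays at 5 up to n = 100, so one look at 100 women gives the same probability as monitoring after each woman.
- p = true proportion with one related, incapacitating reaction of a given type. The documents give no value. I take 8% and 5% as assumptions, and 2.5%, which is the severe fatigue rate in US adults and the highest severe solicited rate quoted for BOOSTRIX in Protocol 2.3.1.
- q = share of those events graded below 3 (assumed). If assessors grade every gap event up, q = 0 and nothing is lost.

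The chance of meeting the rule is P(X ≥ 5) with X ~ Binomial(100, p(1 − q)). For example, p = 8% and q = 25% gives an effective rate of 0.08 × 0.75 = 6% and P = 0.723.

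| p | q = 0 | q = 10% | q = 25% | q = 50% |
|---|---|---|---|---|
| 8% | 0.910 | 0.854 | 0.723 | 0.371 |
| 5% | 0.564 | 0.470 | 0.321 | 0.106 |
| 2.5% | 0.106 | 0.076 | 0.040 | 0.009 |

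If the count is checked after each woman up to all 200, the chance of ever crossing at p = 8% is 0.983, 0.960, 0.875 and 0.499 for the same values of q. Crossings close to 200 leave little enrolment to halt.

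**The case against.** The strongest reply is that the practical effect is small.

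- **No planned test changes.** Fisher's exact test compares any reaction with none; severity is only described. Assessors are blinded, so inconsistent grading should not favour an arm. This stands.
- **The halting figures rest on assumed rates.** The only rate from the documents is 2.5%, for fatigue, a row without the gap; at that rate the rule is seldom met anyway. The 8% case also applies one rate to both arms. If only BOOSTRIX recipients carry it (about 67 of the first 100 women), P(X ≥ 5) at q = 0 is about 63%, not 91%. This stands as a limit on the numbers. But a halting rule exists for the case where reactions are worse than expected, and there the loss is material.
- **Other safeguards exist.** Women are told to report severe reactions (Protocol 7.3), investigators assess and review severity (9.2.1, 15.1), any related SAE halts the study (9.5), and the DSMB reviews Day 8 data at 25% of subjects (9.6.2). A woman this unwell may also report fatigue or myalgia that reaches Grade 3. These reduce the harm, but investigator review still has to apply the same row wording.
- **The gap may be narrow.** Medical intervention is not defined. If it includes oral analgesics or a clinic visit, few incapacitating events fall between grades. This is possible, but the text does not settle it.
- **The higher bar may be deliberate, and a tie-break would be enough.** A deliberate bar would still need a grade for the events below it. A rule to assign the higher grade would close both cells, but it would make some interference with treatment Grade 3, unlike fatigue, myalgia and nausea.

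**Conclusion.** The concern holds. The three rows are wrong as written: two of six combinations have no grade, including the clinically important one, and nothing in the protocol or SAP resolves it. The Manual of Procedures might hold a convention, but it is not among the documents, and it would leave the wording of both uncorrected.

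The coverage result needs no assumptions. The halting effect does. It is nil if assessors always grade up, small at 2.5%, and substantial only if reactions are well above the quoted rates and a sizeable share is graded low. The clinician call and the severity tables can be affected by a single event. This should be corrected, but it does not undermine the planned between-arm comparisons.

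**What to change.** In the feverishness, malaise and arthralgia rows of Protocol Table 5, and the ecchymosis row of Table 3, remove the intervention clause. Grade 1 is then no interference with daily activity, Grade 2 some interference, and Grade 3 prevented activity, in line with fatigue, myalgia and nausea. Make the same change in SAP Table 8, on the data form and in field-worker training. The six combinations become Grades 1, 1, 2, 2, 3, 3, each in exactly one grade.

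Replacing *and* with *or* in Grade 3 is not a good substitute. It would make an event with no interference Grade 3 merely because it was treated, whereas the allergic-reaction row sets Grade 2 as "Localized urticaria OR requires oral therapy".

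The cost is four table rows in each document, the form and the training. Reported Grade 3 rates and clinician calls may rise somewhat. Information on treatment is not lost, since concomitant medications are already recorded at the Day 4 and Day 8 visits.

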9.2.3. Additional Adverse Event Severity Grading

Pulse and blood pressure[#] will be graded as follows:

Table 7: Pulse and Blood Pressure Severity Grading

Physiologic Parameter	Mild (Grade 1)	Moderate (Grade 2)	Severe (Grade 3)
Bradycardia - beats per minute	50 – 54 or 45-50 if baseline <60 bpm	45 – 49 or 40-44 if baseline <60 bpm	< 45 or <40 if baseline <60 bpm
Tachycardia - beats per minute	101 – 115	116 – 130	> 130 or ventricular dysrhythmias
Hypotension (systolic) mm Hg	85-89	80-84	< 80
Hypertension (systolic) mm Hg	141-150	151-160	> 160
Hypertension (diastolic) mm Hg	91-95	96-109	> 109

[#]Pulse and blood pressure assessed on Day 1 prior to the study vaccination will be considered as baseline.

9.2.4. Grading of Specific Adverse Events in the Pregnant Women and their Infants

Table 8: Maternal and Infant Adverse Events

Maternal Adverse Events (Adverse Events during Pregnancy)				
Parameter	Normal	Grade 1	Grade 2	Grade 3
Pregnancy loss (Pregnancy does not result in a live birth)	None	N/A	N/A	Spontaneous abortion or miscarriage
Spontaneous abortion or miscarriage in the first or second trimester of gestation				
Fetal death at or after 20 weeks of gestation (stillbirth)				
Bleeding (vaginal) during pregnancy prior to the onset of labor	None	Spotting or bleeding less than menses	Bleeding like menses or heavier, no intervention indicated	Profuse bleeding with dizziness or orthostatic hypotension, transfusion indicated
Postpartum hemorrhage	EBL ^c ≤500 cc for vaginal delivery or ≤1000 cc after CS or reported as normal	EBL 501-1000 for vaginal delivery or 1001-1500 for CS or reported as slightly increased	EBL >1000 for vaginal delivery or >1500 for CS, with or without mild dizziness, no transfusion required	Hemorrhage at a level for which transfusion of packed cells or any amount of other blood components is indicated
Postabortal endometritis/salpingitis	None	Low grade fever and uterine tenderness, resolved with oral antibiotics	Moderate symptoms, requiring ≤3 days of parenteral antibiotics	Severe symptoms requiring >3 days of IV antibiotics or development of TOA
Preterm rupture of membranes	None	N/A	Preterm rupture but not resulting in delivery before 37 weeks gestation	Preterm rupture resulting in delivery before 37 weeks gestation

Preterm contractions /labor/delivery^e	None Braxton Hicks contractions (as early as second trimester)	Preterm contractions which resolve without medical intervention	Preterm contractions with cervical change which result in medical intervention but not resulting in preterm delivery	Delivery before 37 weeks gestation
Poor fetal growth If infant is small for gestational age on newborn exam: report as NEONATAL OUTCOME based on birth weight (see below)	At or above 10 th percentile	Fetal growth <10 th percentile but ≥3 rd percentile for gestational age by ultrasound	N/A	Fetal growth <3 rd percentile for gestational age by ultrasound
Hypertension, preeclampsia/eclampsia	None	Pregnancy induced hypertension	Preeclampsia	HELLP syndrome, or eclampsia,
Chorioamnionitis	None	Fever (38°C–38.4°C or 100.4°F–100.9°F) with two or more: FHR ^e >160 BPM ^f , maternal HR >120, uterine tenderness between contractions or purulent AF or preterm labor	Same as Grade 1 plus fever 38.5°C–40°C or 101°F–104°F	Criteria for Grade 2 plus fetal distress or fever >40°C or 104°F
Postpartum endometritis	None	Low grade fever and uterine tenderness, resolved with oral antibiotics	Moderate symptoms, treated by ≤3 days of parenteral antibiotics	Severe symptoms treated with >3 days of IV antibiotics, addition of heparin, or operative intervention
Gestational diabetes mellitus	N/A	New onset controlled by diet	New onset with initiation of medical therapy	Uncontrolled despite treatment modification
Clinical AE, pregnancy-related, NOT identified elsewhere in this AE Grading Table	None	Symptoms causing no or minimal interference with usual social & functional activities	Symptoms causing greater than minimal interference with usual social & functional activities	Symptoms causing inability to perform usual social & functional activities

Mode of delivery^f (normal spontaneous vaginal delivery, induced delivery, assisted vaginal delivery, Caesarean Section)	Not reported as AE/SAE. Mode of delivery is a procedure and should not be reported or graded as an AE/SAE. The reason for selecting the mode of delivery (for example: Caesarean Section for severe preeclampsia) should be reported and graded as appropriate.
--	---

**Infant Adverse Events
(Neonatal and Infant Events)**

Parameter	Normal	Grade 1	Grade 2	Grade 3
Preterm birth^g	Born after 36 6/7 weeks gestation	Late preterm: 34 to 36 6/7 weeks gestation	Early preterm: 32 to 33 6/7 weeks gestation	Very or extremely preterm: ≤ 31 6/7 weeks gestation
Birth weight (grams)^g (Small, appropriate, large for gestational age)	Birth weight ≥2500		Low birth weight: 1501-2500	Very low birth weight ≤1500
Report separately poor fetal growth (as above)				
Neonatal complications in a term infant	Normal term infant discharged home with mother after uncomplicated delivery and nursery course	Transient signs and symptoms requiring no interventionⁱ , and resolved spontaneously ^h	Signs/symptoms requiring interventionⁱ but discharged home with mother (± 2 days) , or close to it	Required NICU for more than 1 week, and/or interventions (including surgery) leading to prolonged hospitalization (report SAE) ^j
Clinical AE in the newborn NOT identified elsewhere in this AE Grading Table (postmaturity)	None	Symptoms causing no or minimal interference with usual functional activities	Symptoms causing greater than minimal interference with function and activities	Symptoms causing inability to perform functions or activities
Congenital anomalies/birth defects^m	Variants of normal and minor anomalies are NOT reported, graded or followed as AE, or SAEs. They are collected in the database as part of the medical examination and reported in the Final Study Report.	N/A	N/A	Major congenital anomalies are reported as SAEs.

Abbreviations and definitions:

^a Please refer to 'Definitions of Safety Parameters' for regulatory definition of 'life threatening' that requires reporting of SAE.

^b Even if pregnancy loss does not require obstetrical care, and is a natural outcome of non-viable conception, psychological events around the event require recognition especially in research subjects.

^c EBL: Estimated blood loss.

^d TOA: Tubo-ovarian abscess.

^e For preterm delivery, report two AEs: one for mother and one for infant. Unless specified otherwise in the protocol, only one neonatal AE will be reported for all preterm birth-related problems. Additional AEs will be reported only if infant has unexpected AEs: surgery, congenital anomalies, etc.

^fExamples of complications of delivery that would meet AE/SAE reporting are: maternal death, stillbirth, bleeding placenta previa or abruption that required emergency delivery, etc.

^gPreterm birth and low birth weight carry different risks and will be reported separately (or twice if an infant is both preterm and low birth weight). If gestational age is not known, only birth weight will be reported. Infants will be plotted on the appropriate growth scale for the population being studied and percentage of ‘appropriate’, ‘large’, or ‘small for gestational age’ infants will be reported in the final study report.

^hExamples: transient tachypnea, hypothermia, cephalo-hematoma, bruising. Admitted to normal nursery or observed for less than one day in NICU/SCN.

ⁱExamples: admission to NICU/SCN for physiological causes like hyperbilirubinemia requiring phototherapy, hypoglycemia, suspected but ruled out congenital infection, oxygen via nasal cannula, or NCPAP.

^jExamples: confirmed neonatal infection: bacterial, viral, fungal sepsis, meconium aspiration syndrome on respirator, severe laboratory, or/and clinical signs and symptoms.

^kExamples: perinatal asphyxia: 10 min Apgar scores below 5, shock, critical neonatal laboratory values, etc.

^lPost maturity carries unique, but still not clearly defined risks. Currently, this category should be used to evaluate signs and symptoms related to post-maturity.

^mInvestigators should consult the protocol and/or the MOP for a list of ‘major congenital anomalies’ and report them as SAE. Minor anomalies (also listed in the protocol and/or MOP) are structural findings that do not have surgical, medical or cosmetic importance. Minor physical features that typically occur in more than 4% of newborn infants are considered ‘variants’ of normal, while ‘minor anomalies’ occur in less than 4% of infants. If in doubt: review referenced articles in Rasmussen et al Clin Infect Dis 2014 p S 428ff²⁹ and/or consult DMID.

AE: Adverse Events

CS: Cesarean Section

HELLP syndrome: Group of symptoms that occur in pregnant women who have: hemolysis (H); elevated liver enzymes (EL); low platelet count (LP).

